#### CONFIDENTIAL

#### Procedure Treatment Period (Visit Window is ± 1 Week) Exit/ EW Visit Visit 32 33 37 34 35 36 38 39 40 41 42 43 44 Week of study 124 128 132 136 140 144 148 152 156 160 164 168 172 Safety Assessments **Concomitant Medication** X X X Х X X X X X X X X X Physical Examination X Vital Signs X Х X X Х Х Х X X X Х X X X Х Х 12-lead ECG Adverse Events X Х X X X X Х X X X X X Х X X X X X X X X X X X Serious Adverse Events X X Laboratory Assessments Immunogenicity Х Х X X X Hematology Chemistry X Х X X X X Liver Analytes U U U U U U U U U U U U U Pregnancy Test Efficacy Assessments X X Exacerbation review Х X Х Х Х Х X Х Х X X X X X X Asthma Control X Questionnaire-5 Х Spirometry Х Х Worksheets/IP/eCRF Administer Mepolizumab X X Х X X Х X Х X Х X X 100mg SC Dispense Paper Worksheet Х Х Х Х Х Х Х X X Х X Х Х Collect Paper Worksheet X Х X Х X X Х X X X X X X Register IVRS/IWRS X Х X Х Х X X Х Х X Х Х Х Complete eCRF X Х X X X X Х X X X X X X

2. All laboratory assessments to be completed prior to dosing

3. Pregnancy test (all females of childbearing potential) U = Urine

4. In the event a subject withdraws early at a scheduled visit, all study procedures scheduled for the Exit Visit (Visit 44) should be performed at this visit instead. In the event a subject withdraws between visits, the subject should be asked to return to the clinic as soon as possible to complete the Exit Visit procedures.

### 11.2. Appendix 2: Assessment Windows

### 11.2.1. Assessment Windows

In some circumstances certain Visit 1 assessments will not be performed and assessments will be copied from either Visit 14 (Exit Visit) or Visit 15 (Follow Up) from the preceding study MEA115661. Refer to Section 5.2 for more details.

All other visits are scheduled to take place as specified in Appendix 2: Time & Events. Measurements outside visit windows will not be excluded from analyses. For all clinic visits, nominal visit days and times will be used for reporting, such that if a subject recorded values that were outside of the  $\pm 7$  day window for a visit they will still be reported under that visit.

### 11.2.2. Early Withdrawal Visits

If a subject withdraws from the study at a scheduled visit (i.e. completes an Early Withdrawal), where endpoint data were scheduled to be collected, the data will be summarised and analysed (as appropriate) together with data from subjects who did not withdraw from the study. If a subject withdraws from the study at a scheduled visit at which endpoint data were not scheduled to be collected, or if a subject withdraws between scheduled visits, data will be slotted to the nearest adjacent visit where the endpoint data was scheduled to be collected (if data at that visit were not recorded) according to the Time and Events schedule (Appendix 1: Schedule of Activities).

For example, if a subject prematurely withdraws from the study and completed the Early Withdrawal Visit at Visit 6 (Week 20) and completes an Early Withdrawal Visit which includes an FEV1 assessment, the FEV1 data collected will need to be re-assigned to an adjacent visit where FEV1 data is scheduled for collection. In this case the FEV1 data will be reassigned to Visit 7 (Week 24) (if data at that visit were not recorded) as this is the closest nominal visit at which collection of FEV1 data is scheduled.

### 11.2.3. Unscheduled Visits

For unscheduled visits, similar logic will be applied. If a subject has an unscheduled assessment then this data would be slotted to the closest adjacent scheduled visit but only if information does not already exists at that visit. If an unscheduled visit occurred between two scheduled visits for which data has been reported, then the data from the unscheduled visit will remain in the unscheduled visit and will not be used in summary tables and analyses (except for endpoints using any post-baseline data) but will be presented in any relevant listings.

After Visit 31 (Week 120) all the visits will be collected in an unscheduled manner. As a result, all assessments following Visit 31 will be slotted to the appropriate scheduled visit using the closest assessment to the expected/target visit date.

### 11.3. Appendix 3: Treatment Phases

### 11.3.1. Treatment Phases (Efficacy Data)

Exacerbation data and efficacy data collected at scheduled visits (including: ACQ-5 Questionnaire, PFT and Blood Eosinophils) will be classified according to time of occurrence/assessment relative to the first and last date of mepolizumab in study 201312 and the attendance dates of specific visits.

Treatment Phase	Definition
Pre-Treatment	Date & Time < First dose of mepolizumab Date & Time in study 201312
On-Treatment	First dose of mepolizumab in study 201312 $\leq$ Date & Time $\leq$ Earliest of (1) or (2):
	(1) Last dose of mepolizumab Date in study 201312 + 28 days or
	(2) Early Withdrawal Visit Date
Post-Treatment	Date & Time > Earliest of (1) or (2):
	(1) Last dose of mepolizumab in study 201312 + 28 days or
	(2) Early Withdrawal Visit Date

### 11.3.2. Treatment Phases (Adverse Events)

Adverse events will be classified according to time of occurrence relative to the first and last date of the study treatment in study 201312.

Treatment Phase	Definition
Pre-Treatment	AE Onset Date & time < First dose of mepolizumab in study 201312 If mepolizumab treatment in study 201312 is never started then all AEs will be
	classified as pre-treatment.
On-Treatment	First dose of mepolizumab in study 201312 $\leq$ AE Onset Date & Time $\leq$ Last dose of mepolizumab in study 201312 + 28 Days.
	If an AE start date is missing or partial then the AE will be considered on-treatment unless there is evidence to the contrary (e.g. month/year of onset date is present and is earlier than the month/year of First dose of mepolizumab in study 201312).
Post-Treatment	AE Onset Date & time > Last dose of mepolizumab in study 201312 + 28 days

### 11.3.2.1. Adverse Events Data Derivations

Treatment Phase	Definition	
Onset Time	If First dose of mepolizumab in study 201312 > AE Onset Date = AE Onset Date - First	
Since Ist Dose	dose of mepolizumab in study 201312	
(Days)	If First dose of mepolizumab in study 201312 $\leq$ AE Onset Date = AE Onset Date - First	
	dose of mepolizumab in study 201312 +1 day	
	If First dose of mepolizumab in study 201312 or AE Onset Date is missing = missing.	
Duration (Days)	AE Resolution Date - AE Onset Date + 1	
Drug-related	If relationship is marked 'YES' on Inform/eCRF OR value is missing.	

### 11.3.3. Treatment Phases (Concomitant Medications)

Concomitant medications will be classified according to time of occurrence relative to the first and last date of the study treatment in study 201312.

A medication will be summarised in every treatment/study phase in which it was taken, so for example a medication that was started during treatment and stopped post treatment will appear in both the during treatment and post treatment tables.

Treatment Phase	Definition
Taken During	If Con-med Start Date < First dose of mepolizumab in study 201312 and Con-med
Treatment	Stop Date $\geq$ First dose of mepolizumab in study 201312
	or
	If First dose of mepolizumab in study 201312 $\leq$ Con-med Start Date $\leq$ Last dose of mepolizumab in study 201312+28 days
	If the con-med start or stop date is missing or partial then the con-med will be considered on-treatment unless there is evidence to the contrary (e.g. month/year of con-med stop date is present and is before the month/year of the first dose of mepolizumab in study 201312).
Started During	Subset of con-meds taken during Treatment for which:
Treatment	First dose of mepolizumab in study 201312 $\leq$ Con-med Start Date $\leq$ Last dose of mepolizumab in study 201312 + 28 days
Taken Post Treatment	Last dose of mepolizumab in study 201312+ 28 days < Con-med Stop Date

## 11.4. Appendix 4: Data Display Standards & Handling Conventions

### 11.4.1. Reporting Process

Software

oonware		
The currently supported versions of SAS software will be used.		
Reporting Area		
HARP Server	: uk1salx00175	
HARP Compound	: /arenv/arprod/sb240563/ mid201312 /final	
Quality Control	: /arenv/arprod/sb240563/ mid201312/final/documents	
(QC) Spread sheet		
Analysis Datasets		
Analysis datasets will be created according to CDISC standards.		
• For creation of ADaM datasets (ADCM/ADAE), the same version of dictionary datasets will be		
implemented for conversion from SI to SDTM.		
Generation of RTF Files		

#### Generation of RTF Files

RTF files will be generated only for summary tables.

#### 11.4.2. Reporting Standards

#### General

 The current GSK Integrated Data Standards Library (IDSL) will be applied for reporting, unless otherwise stated

(IDSL Standards Location: https://spope.gsk.com/sites/IDSLLibrary/SitePages/Home.aspx)

- 4.03 to 4.23: General Principles
- 5.01 to 5.08: Principles Related to Data Listings
- 6.01 to 6.11: Principles Related to Summary Tables
- 7.01 to 7.13: Principles Related to Graphics

#### Formats

- GSK IDSL Statistical Principles (5.03 & 6.06.3) for decimal places (DP's) will be adopted for reporting of data based on the raw data collected, unless otherwise stated.
- Numeric data will be reported at the precision collected on the eCRF.
- The reported precision (decimal places) will follow the IDSL statistical principles but may be adjusted to a clinically interpretable number of decimal places.

#### Planned and Actual Time

- Reporting for tables, figures and formal statistical analyses:
  - Nominal visits (planned time relative to start of dosing) will be used in figures, summaries, statistical analyses and calculation of any derived parameters, unless otherwise stated.
  - The impact of any major deviation from the planned assessment times and/or scheduled visit days on the analyses and interpretation of the results will be assessed as appropriate.
- Reporting for Data Listings:
  - Planned and actual time relative to study drug dosing will be shown in listings (Refer to IDSL Statistical Principle 5.05.1).
  - Unscheduled or unplanned readings will be presented within the subject's listings.
  - Scheduled visits outside the protocol defined time-windows (i.e. recorded as protocol deviations) will be included in listings, summaries and statistical analyses.

п

-

Unscheduled Visits	Unscheduled Visits		

 
When possible unscheduled assessments will be slotted to the closest adjacent scheduled visit. If an unscheduled visit occurs between two completed scheduled visits, the data from the unscheduled visit will not be used in summary tables which are based on by-visit assessments. The information from the unscheduled visit will be included in 'any time post-baseline' summaries and will also be presented in any relevant listings. Note additionally all assessments following Visit 31 will be slotted to the appropriate scheduled visit. See Appendix 2: Assessment Windows for further details.
 
			
Descriptive Summary Statistics			
Continuous Data	Refer to IDSL Statistical Principle 6.06.1		
Categorical Data	N (number of subjects in the treatment group), n (number of subjects with non- missing values), frequency, %		
Graphical Displays			
Refer to IDSL Statistical Principals 7.01 to 7.13.			

### 11.5. Appendix 5: Derived and Transformed Data

### 11.5.1. General

Multiple Measurements at One Analysis Time Point

• There are no scheduled multiple measurements, however, if multiple measurements are recorded at a given time point the following process will be followed, unless a process for selection of the measurement for the visit is specified:

• Mean of the measurements will be calculated and used in any derivation of summary statistics but if listed, all data will be presented.

• Subjects having both High and Low values for Normal Ranges at any post-baseline visits for safety parameters will be counted in both the High and Low categories of 'Any visit post-baseline' row of related summary tables.

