6.3.10. Other Safety Outcomes

6.3.10.1. Laboratory Assessments

All protocol required laboratory assessments, as defined in the Time and Events Table ([Appendix 1](#) Time and Events Table), will be taken pre-dosing and will be sent to the central laboratory, Quest Diagnostics for analysis (details provided in the SPM). Laboratory assessments must be conducted in accordance with the Central Laboratory Manual and Protocol Time and Events Schedule. Laboratory requisition forms must be completed and samples must be clearly labelled with the subject number, protocol number, site/centre number, and visit date. Details for the preparation and shipment of samples will be provided by Quest Diagnostics. Reference ranges for all safety parameters will be provided to the site by Quest Diagnostics. The central laboratory will fax laboratory results to the Investigator and will transmit the results electronically to GSK.

At the discretion of the Investigator, additional samples may be taken for safety reasons. If additional non-protocol specified laboratory assessments are performed at the institution's local laboratory and result in a change in patient management or are considered clinically significant by the investigator (e.g., SAE or AE or dose modification) the results must be recorded in the subject's CRF. Refer to the SPM for appropriate processing and handling of samples to avoid duplicate and/or additional blood draws.

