Labora	tory: Chemistry	/					
2.53.	AT	LB1	Summary of Chemistry Changes from Baseline	ICH E3 Includes Baseline values.	SAC		
2.54.	AT	LB3	Summary of Chemistry Results (Changes from Baseline Relative to the Normal Range)	See also format of Safety Table 7.36 (MEA115588 'final reporting effort)	SAC		
2.55.	AT	LB3	Summary of Chemistry Results (Changes from Baseline Relative to the Reference Range [Potential Clinical Importance])	See also format of Safety Table 7.36 (MEA115588 'final reporting effort)	SAC		
Labora	tory: Haematol	ogy					
2.56.	AT	LB1	Summary of Haematology Changes from Baseline	ICH E3 Includes baseline values.	SAC		
2.57.	AT	LB3	Summary of Haematology Results (Changes from Baseline Relative to the Normal Range)	See also format of Safety Table 7.42 (MEA115588 'final reporting effort)	SAC		
2.58.	AT	LB3	Summary of Haematology Results (Changes from Baseline Relative to the Reference Range [Potential Clinical Importance])	See also format of Safety Table 7.42 (MEA115588 'final reporting effort)	SAC		
Labora	tory: Hepatobil	iary (Liver)		•			
2.59.	AT	LIVER10	Summary of Subjects Meeting Emergent Hepatobiliary Laboratory Abnormality Criteria	IDSL	SAC		
ECG	·						
2.60.	AT	EG1	Summary of ECG Findings	IDSL	SAC		
2.61.	AT	EG2	Summary of Change from Baseline in ECG Values by Visit	Includes baseline values.	SAC		
2.62.	AT	SHELL	Summary of Actual and Change From Baseline QTc(F) Values by Category (msec)		SAC		

Safety:	Safety: Tables								
No.	Population	IDSL / Example Shell	Title	Programming Notes	Deliverable				
2.63.	AT	SHELL	Summary of Actual and Change From Baseline QTc(B) Values by Category (msec)		SAC				
Vital Si	gns								
2.64.	AT	VS1	Summary of Change from Baseline in Vital Signs	ICH E3 Includes Baseline values.	SAC				
Immun	ogenicity								
2.65.	AT	SHELL	Summary of ADA Assay Results	See format of Other Assessments Table 8.01 (MEA115588 'final' reporting effort)	SAC				
2.66.	AT	SHELL	Summary of Treatment Emergent ADA Assay Results		SAC				
2.67.	AT	SHELL	Summary of NAb Assay Results	See format of Other Assessments Table 8.02 (MEA115588 'final' reporting effort)	SAC				

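### Laboratory repeats stored under one visit are averaged before classification, so a normal repeat can remove an abnormal result from the normal-range and PCI tables

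*SAP*

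**What the plan says.** SAP 11.5.1 opens its rule on multiple measurements by noting that "There are no scheduled multiple measurements", so the rule concerns only ad hoc repeats. The default applies "unless a process for selection of the measurement for the visit is specified", and reads: "Mean of the measurements will be calculated and used in any derivation of summary statistics but if listed, all data will be presented". The next bullet deals with extremes across visits: "Subjects having both High and Low values for Normal Ranges at any post-baseline visits for safety parameters will be counted in both" categories of the any-visit post-baseline row.

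SAP 11.4.2 places categorical data (frequency and percentage) under descriptive summary statistics, next to continuous data. The default therefore reads naturally onto the categorical laboratory tables: 2.54 and 2.57 (normal range) and 2.55 and 2.58 (PCI limits from SAP 11.7.1).

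Other rules limit its reach:
- **Unscheduled visits (SAP 11.2.3 and 11.4.2).** An unscheduled result is slotted only into a visit with no data. If it falls between two completed visits, "the data from the unscheduled visit will not be used in summary tables which are based on by-visit assessments". It does enter the any-time post-baseline summaries.
- **After Visit 31 (SAP 11.2.3).** The assessment closest to the target date is selected.
- **QTc categories (SAP 11.5.4).** Individual maxima are used.
- **Baseline (SAP 5.3).** The latest pre-dose assessment is taken.

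Protocol 6.3.10.1 says that, at the investigator's discretion, "additional samples may be taken for safety reasons". Local results that are clinically significant or change management must be recorded in the CRF. It does not say to which time point such results are assigned.

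**The concern.** Averaging suits a continuous by-visit summary. It does not suit a table whose purpose is to count subjects who crossed a limit. If two results share a time point and one is abnormal, the mean can fall inside the limit, and the subject then disappears from the count for that visit. If that was the subject's only abnormal result, the subject also drops out of the any-visit row.

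The rule also sits awkwardly beside its neighbour. A subject who is High at one visit and Low at another is counted in both categories, but a subject with both at one time point may be counted in neither.

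Laboratory parameters are a protocol endpoint, and SAP section 7 names long-term safety as the main interest. At stake is whether these four tables report every abnormal result that the study recorded.

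**Working it through.** The plan states no figure to reproduce. The check applies the averaging rule to the SAP 11.7.1 limits.

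**Formula.** Let A be the first result, r the repeat and T the limit. The mean (A + r)/2 is flagged high only if A > 2T - r, and flagged low only if A < 2T - r.

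**Inputs.** T comes from SAP 11.7.1. The documents give no normal ranges, so r is an assumption: the low, middle and high points of an ordinary adult range.

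| Analyte and PCI limit T | Assumed r (low / mid / high) | First result needed, 2T - r |
|---|---|---|
| Potassium > 6.5 mmol/L | 3.5 / 4.2 / 5.1 | > 9.5 / 8.8 / 7.9 |
| Potassium < 2.8 mmol/L | 3.5 / 4.2 / 5.1 | < 2.1 / 1.4 / 0.5 |
| Sodium > 160 mmol/L | 135 / 140 / 145 | > 185 / 180 / 175 |
| Sodium < 120 mmol/L | 135 / 140 / 145 | < 105 / 100 / 95 |
| Calcium > 3.24 mmol/L | 2.1 / 2.4 / 2.6 | > 4.38 / 4.08 / 3.88 |
| Haemoglobin < 71 g/L | 120 / 140 / 170 | < 22 / 2 / -28 |
| Glucose < 2.2 mmol/L | 3.9 / 5.5 / 7.0 | < 0.5 / -1.1 / -2.6 |
| Haematocrit < 0.201 | 0.36 / 0.42 / 0.50 | < 0.042 / -0.018 / -0.098 |
| Platelets < 31 x10^9/L | 150 / 250 / 400 | < -88 / -188 / -338 |
| WBC < 1.1 x10^9/L | 4 / 6 / 11 | < -1.8 / -3.8 / -8.8 |
| Phosphorus < 0.32 mmol/L | 0.8 / 1.1 / 1.5 | < -0.16 / -0.46 / -0.86 |

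**When a low flag cannot survive.** Results cannot be negative, so any repeat of at least 2T removes a low flag whatever the first result was.
- Platelets 2 x 31 = 62, WBC 2 x 1.1 = 2.2, phosphorus 2 x 0.32 = 0.64. All three lie below the assumed normal range, so every normal repeat removes the flag.
- Haemoglobin 2 x 71 = 142, glucose 2 x 2.2 = 4.4, haematocrit 2 x 0.201 = 0.402. These lie inside the assumed range, so the outcome depends on the repeat.

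**Examples.**
- Potassium 6.8 then 4.2: (6.8 + 4.2)/2 = 5.5, not flagged.
- Platelets 20 then 250: (20 + 250)/2 = 135, not flagged.
- Sodium 165 then 140: (165 + 140)/2 = 152.5, not flagged.
- Potassium 2.5 and 6.9 at one time point: (2.5 + 6.9)/2 = 4.7, and both flags are lost.

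Using the most extreme individual value in each direction keeps every one of these flags.

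**Direction.** A mean is never more extreme than the most extreme value in it. With baseline fixed by SAP 5.3, averaging post-baseline results can leave the flagged counts unchanged or lower them, compared with counting each individual result.

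**The case against.** The strongest reply is that the usual retest never meets this rule. Protocol samples go to a central laboratory, so a retest prompted by the result would normally be a later draw. If it is recorded as an unscheduled visit and the adjacent visits have data, the abnormal result stays in its by-visit table and the repeat is not averaged with it. This stands, and it confines the problem to repeats stored under the same nominal visit.

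Nor is averaging universal. The default yields to a specified selection process, and such processes exist for baseline, for visits after Visit 31 and for QTc. This stands too, but none of them covers post-baseline laboratory repeats up to Visit 31.

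The values are also not lost from the study. Listings show all data, Listing 47 covers subjects with any PCI value, and Protocol 6.3.3 makes clinically significant abnormalities adverse events, apart from those due to the underlying disease and no worse than expected. This is largely right. However, Listing 47 is the only general laboratory listing. An out-of-range result short of a PCI limit may therefore appear in no planned display once it is averaged out of Table 2.54 or 2.57.

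The downward direction depends on the benchmark. Against using the first result alone, averaging can add a flag: potassium 6.0 then 7.4 gives 6.7, above 6.5. That is correct, and it is why the comparison here is with counting every individual result. The extreme-value rule will in turn count some laboratory artefacts.

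Finally, the four tables use the sponsor's standard LB3 shell, which may have its own record-selection rule. It is not in the documents, so this can be neither confirmed nor excluded. The study is also single-arm and descriptive, so no decision rule turns on these counts.

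**Conclusion.** The point holds within limits. As written, SAP 11.5.1 averages post-baseline laboratory results that share a time point up to Visit 31 before Tables 2.54, 2.55, 2.57 and 2.58 are derived. One normal repeat can therefore remove a normal-range or PCI flag. For low platelets, WBC and phosphorus it always does so across the assumed range; for the other limits it depends on both values. Severity is minor to moderate: the stated rule is wrong for these tables, but how often it would operate is unknown.

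A reader might infer three stronger things that the documents do not support:
- **That retests generally erase the result that prompted them.** The unscheduled-visit rules keep separately recorded repeats apart from a visit that already has data.
- **That averaging governs every safety summary.** QTc categories use individual maxima, and visits after Visit 31 use the closest assessment.
- **That a low flag becomes impossible for glucose, haematocrit or haemoglobin as well.** At the low end of the assumed range (3.9 mmol/L, 0.36, 120 g/L) the required first result is still positive (0.5, 0.042, 22).

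The conclusion assumes that some repeats are entered under the same nominal visit and that no rule in the LB3 standard overrides the SAP text. The sizes rest on the assumed normal repeats.

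**What to change.** In SAP 11.5.1, limit averaging to continuous by-visit laboratory and vital-sign summaries. Add that normal-range and PCI laboratory categories, including the any-visit post-baseline row, use the most extreme individual value in each direction at each post-baseline time point, and that a subject with both a High and a Low value there is counted in both. If the LB3 standard already selects records this way, cite it instead.

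Leave the QTc categories under SAP 11.5.4 as individual maxima. The triplicate averaging in Protocol 4.4.3.1.1 is a discontinuation criterion, not an analysis rule, and should not be carried into these tables.

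The cost is one or two sentences and a change to record selection in four tables. The downside is a few more flagged values, some of them laboratory artefacts; PCI-level ones can be examined beside their repeats in Listing 47.
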